A randomized control trial of furosemide or placebo with usual antihypertensives in the antepartum management of severe hypertension with wide pulse pressure Protocol Number I Version 2 02/21/20

Principal Investigator: [name] [name], MPH, MCR

Sub-Investigator: [name]

Research Site: Kapi'olani Medical Center for Women and Children [name] [contact]

Version 2

Protocol Number I

Protocol Title: A randomized control trial of furosemide or placebo with usual antihypertensives in the antepartum management of severe hypertension with wide pulse pressure

Version Date: 2/21/20 Protocol Number: I

Principal Investigator: [name] [name]

Sub-Investigator(s): [name]

Research Site(s): Kapiolani Medical Center for Women and Children

Section I: Purpose and Background

1. Purpose

Primary objective: To determine whether the addition of intravenous furosemide with usual antihypertensives is associated with a reduction in mean systolic blood pressure from baseline compared to treatment with placebo plus usual antihypertensives (intravenous labetalol, intravenous hydralazine, or oral immediate release nifedipine) for the management of severe antepartum hypertension.

Secondary objectives:

To determine whether the addition of intravenous furosemide with usual antihypertensives is associated with a reduction in mean diastolic blood pressure compared to treatment with placebo plus usual antihypertensives listed above.

2. Background

Introduce and provide support for the research being proposed. Basic information relevant to the context of the research question and study design should be included in this section. Additionally, this section should be written in a way that a person who is not an expert in the field can understand.

Blood pressure is a measure of blood flow and resistance in blood vessels. In normal pregnancy, total blood volume increases while systemic vascular resistance decreases, thereby leading to an overall reduction in blood pressure with return to baseline at term. Hypertensive disorders in pregnancy, including preeclampsia, are a polymorphic syndrome characterized by elevated blood pressures which can affect multiple organ systems¹. Although the exact mechanism of preeclampsia has yet to be determined, previous studies have shown that there may be two distinct phenotypes – one characterized by vasoconstriction and diminished micro-circulation and the other involving a hyperdynamic high cardiac output state^{2,3}.

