Study Procedures

- 1. Antepartum patient diagnosed with a hypertensive disorder in pregnancy.
- 2. Patient approached for study participation and informed consent obtained if interested.
- 3. Patient develops severe range BP (SBP>160 and/or DBP>110) with increased pulse pressure (>60mmHg). This will be considered baseline BP.
- 4. When ordering provider's choice of antihypertensive, pharmacy notified that patient is study participant and randomizes patient by choosing from sequential opaque envelope.
- 5. a. Patient randomized to treatment arm and receives 40mg /4mL IV furosemide in addition to usual antihypertensive.
 - b. Patient randomized to placebo and receives 4mL normal saline in addition to usual antihypertensive.
- 6. Blood pressure check every 15 minutes after administration of furosemide/placebo for four recordings (15, 30, 45, 60 minutes)

2. Data analysis

Specify statistical and analytical methods (statistical power, sample size, significance level, etc.).

The primary outcome variable is reduction in mean systolic BP during the 1-hour period after drug administration. BP will be taken every 15 minutes for 1 hour and averaged. Intention-to-treat analysis will be performed. This study will use a two-sided t-test with the null hypothesis set at the standard significance level (p –value < 0.05), to determine if the addition of furosemide to usual antihypertensive significantly reduces blood pressure.

Change in average BP from baseline will be tested comparing the group receiving furosemide and the group receiving placebo using Mann-Whitney U, as BP usually presents as a non-parametric continuous variable. Multivariate regression will be used to adjust for potential confounders, such as maternal age, BMI, diabetes, baseline BP, antihypertensive chosen by the primary obstetrician, number of doses of antihypertensive, and gestational age. Comparative testing will be done to explore differences between the furosemide and placebo groups. Continuous variables satisfying the assumption of normality will be tested using the Student t-test and means and standard deviations will be reported. Otherwise, variables will be tested using the Mann-Whitney U test and will be reported using medians and interguartile ranges. The x2 or

Version 2

Protocol Number I

Fisher exact test will be utilized to test categorical variables and sample sizes and percentages will be reported.

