A power calculation was completed using OpenEpi, Version 3, open source calculator—SSMean. The assumption of normality and that both groups will have the same common variance was applied. We set the standard deviation value as 20mmHg in the power calculation, which is based on pilot data from our own practice as well as data found in a randomized clinical trial using furosemide versus placebo (Ascarelli et al, Ob/Gyn 2005). A 15mmHg reduction in mean systolic blood pressure in the placebo group compared with the IV furosemide group was considered to be clinically significant as this represents an attainable, yet safe reduction from severe to mild range blood pressure. Using the 2-group Student t-test of equal means, 28 patients per study arm for a total of 56 patients would be required to detect a difference of 15mmHg with 80% power and a significance level of p=0.05. Once data has been collected, we will test for normality and use the appropriate statistical tests.

To account for patients who withdraw from the study or who need to be excluded after consent, 35 per arm or 70 total patients are to be enrolled. A randomization schedule will be created using block randomization with 10 blocks of 10 participants allocating randomization numbers to drug or placebo. The numbers will be sequentially assigned to participants by the pharmacist on duty. The hospital pharmacy will maintain the master list of the randomization log with patient study identifiers.

Data monitoring

Describe data monitoring methods for studies with more than minimal risk (i.e. data monitoring committee). Explain adverse event reporting procedures.

This is a greater than minimal risk study. Adverse events will be reported to the sub-investigator and primary investigator by the nurse and/or the obstetric provider. Furthermore, the sub-investigator will be actively following study participants closely to monitor for adverse events. If found, these will be reported to the institutional review board according to their reporting polices.

3. Data storage, security, and confidentiality

Describe where data will be stored and how data will be secured during the study. Provide information on confidentiality measures (coding, storage mechanisms, etc.). Indicate who will have access to the data and how the data will be used. If subject identifiers will be released, describe to whom and for what purpose the data will be released.

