
Should a subject decide not to participate in the study, they will receive the standard of care for severe hypertension, which typically includes IV labetalol, IV hydralazine, or oral immediate-release nifedipine. However, furosemide is an adjunct that may be administered to the patient per the primary clinician's decision, unrelated to the study.

Section V: Subject Identification, Recruitment and Consent/Assent (If you are requesting a waiver of consent this section can be deleted)

Method of subject identification and recruitment
 Describe how subjects will be identified and recruited. Include steps to minimize
 undue influence if recruitment includes an investigator's students, employees,
 and/or patients.

Contact will be initiated in person at the time of severe range blood pressure and meeting inclusion criteria by the antepartum care provider. If eligible, individuals who are involved in the study and identified as key study personnel will provide information about the study to the subject and if the subject is interested will proceed with obtaining informed consent. Subjects will be informed of the voluntary nature of the study and informed of alternative treatment options.

2. Consent process

Version 2

Protocol Number I

List study team members authorized to obtain consent and describe the process of informed consent.

Informed consent will be primarily conducted by the sub-investigators, principal investigator, and trained residents and fellows who have completed the necessary training for research clearance. The subject will be approached with study information as close to the time at which she meets inclusion criteria, which in many cases will be at the time of admission. If the study participant is not ready to make a decision regarding their participation at the time of informed consent, then the study personnel will return later that day or the next. The informed consent process will consist of reviewing the informed consent documents and asking the subject a series of questions to ensure comprehension (see subject/representative comprehension below).

3. Subject capacity (if applicable)

Describe how capacity will be assessed and by whom. State the anticipated degree of impairment relative to the subject's ability to consent.

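### One fixed block size of 10, written into the protocol of a single-site diuretic trial, could make some upcoming allocations partly predictable; varying and withholding the sizes is a cheap improvement

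*Combined protocol and SAP*

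**What the plan says.** **Randomisation.** Section III.2 (Data analysis) gives the whole scheme in one sentence: "A randomization schedule will be created using block randomization with 10 blocks of 10 participants allocating randomization numbers to drug or placebo". It also says that "35 per arm or 70 total patients are to be enrolled". There is one site: "Research Site(s): Kapiolani Medical Center for Women and Children". No stratification, varying block size or restriction on who knows the size is described.

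**Concealment and masking.** Under Section III.1 the pharmacy opens sequentially numbered opaque envelopes, and under Section III.2 it keeps the master list. Provider, nurse and patient are described as blinded because both solutions are clear and colourless. Section I.2 describes furosemide as a diuretic with onset at 5 minutes, peak effect at 30 minutes and a 2-hour duration. Section III.1 lists urine output as a daily routine measurement.

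**Who does what.** Section V.2: "Informed consent will be primarily conducted by the sub-investigators, principal investigator, and trained residents and fellows". The Data monitoring paragraph adds that "the sub-investigator will be actively following study participants closely to monitor for adverse events". Section V.1 has the antepartum care provider making first contact when severe-range pressure occurs. The primary obstetric provider chooses the antihypertensive and, in step 4 of the Study Procedures, orders it as the envelope is drawn.

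**The concern.** Opaque envelopes hide the next allocation fully only while earlier allocations stay unknown. If the block size is known and earlier arms can be inferred, the remaining composition of the block becomes informative, most of all towards its end. A diuretic compared with 4 mL of saline offers a plausible clue that matching the appearance of the solutions does not cover.

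Two decisions could be affected. One is whether and when a woman is approached. Section IV.5 notes that furosemide may be given outside the study at the clinician's discretion, so a clinician who expects placebo has an alternative to referral. The other is the choice of co-treatment, which acts directly on systolic pressure over the one-hour outcome window. Intention-to-treat analysis does not correct selection that happens before randomisation.

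**Working it through.** **1. The plan's own figures.** "We set the standard deviation value as 20mmHg in the power calculation"; the difference is 15 mmHg, power 80%, two-sided alpha 0.05. By the normal approximation, n per arm = 2 × [20 × (1.960 + 0.842) / 15]² = 27.9, so 28. Then 28 / 0.80 = 35 per arm, 70 in total. The stated 28, 56 and 70 reproduce. Seventy women fill exactly 70 / 10 = 7 blocks.

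**2. Inputs for predictability.** Block size 2m = 10, so m = 5. A 5:5 split within each block is implied by 35 per arm but not stated. The accuracy q of inferring a past allocation is **not in the documents**. It is an assumption, and a range is shown.

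**3. Upper bound: size known, every past allocation inferred correctly (q = 1).**
- Certain allocations per block = 2m/(m+1) = 10/6 = 1.67, or 16.7%. Over 7 blocks this is 11.7 of 70.
- Correct best guesses per block = m + 2^(2m−1)/C(2m,m) − 1/2 = 5 + 512/252 − 0.5 = 6.53, or 65.3%. Over 7 blocks this is 45.7 of 70, against 35 by chance.
- By position: 1st 50%; 2nd and 3rd 55.6%; 4th and 5th 59.5%; 6th and 7th 64.3%; 8th and 9th 72.2%; 10th 100%.

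Enumerating all C(10,5) = 252 sequences gives the same results.

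**4. Imperfect inference.** Each past allocation is read correctly with probability q, and the guesser makes the best Bayes guess within the block. The number of past women in a given arm is hypergeometric, and the signals are binomial given that number.

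| q | Guessed correctly, all positions | Guessed correctly, 10th position | Certain |
|---|---|---|---|
| 1.0 | 65.3% | 100% | 16.7% |
| 0.9 | 59.2% | 70.7% | 0 |
| 0.8 | 55.9% | 60.8% | 0 |
| 0.7 | 53.7% | 56.1% | 0 |
| 0.6 | 51.8% | 52.8% | 0 |
| 0.5 | 50% | 50% | 0 |

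**5. Effect of varying the size.** Trials of 70 were simulated with blocks drawn at random from 8, 10 and 12. The guesser knows the set of sizes but not their order. The simulation error is about 0.2 points on the guess rates for q below 1, and smaller at q = 1.

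| q | Fixed 10, guessed correctly | 8/10/12, guessed correctly | Allocations predictable at 80% or more: fixed 10 → 8/10/12 |
|---|---|---|---|
| 1.0 | 65.3% | 64.8% | 19% → 12% |
| 0.95 | 61.9% | 60.2% | 10% → 0.4% |
| 0.9 | 59.2% | 57.8% | 2% → 0.1% |
| 0.8 | 55.9% | 55.2% | 0 → 0 |
| 0.7 | 53.7% | 53.1% | 0 → 0 |

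With perfect inference, certain allocations fall from 16.7% to 1.3%. The fall in average guessing lies between 65.3 − 64.8 = 0.5 and 61.9 − 60.2 = 1.7 points. Shorter blocks are worse on this measure. With perfect inference, sizes 4/6/8 give 67.8% correct guessing, and a fixed size of 4 gives 70.8% with 33.3% certain.

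**The case against.** The case against is substantial, and most of it limits the point.

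- **Concealment is otherwise sound.** The pharmacy opens opaque sequential envelopes and holds the list. A guesser would have to track the position in the block across all participants. This stands.
- **Unmasking by diuresis is not shown.** The effect lasts about two hours, while routine urine output is a daily figure, so the signal may be weak. This also stands. Once inference is at all imperfect, no allocation is certain.
- **Order of events.** In the Study Procedures, consent (step 2) comes before severe pressure (step 3) and randomisation (step 4). For women enrolled that way, the pressure event decides who takes the next envelope. Section V.1 also describes contact at the time of severe pressure, so this route is narrowed, not closed. The co-treatment route exists under either order.
- **Planned adjustment.** The regression in Section III.2 includes baseline pressure, antihypertensive chosen, number of doses and gestational age. It addresses measured differences only, and it is separate from the planned two-group comparison.
- **The fix hardly changes average guessing.** This is true. Its gain is in certain and high-confidence predictions.

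A reader might infer more than the text supports. Nothing says the block size was public during enrolment, or that bedside staff knew it. Close follow-up is stated for the sub-investigator only, not for residents and fellows. The primary obstetric provider, who chooses the antihypertensive, is not listed among those obtaining consent. Ten blocks of 10 give 100 slots for 70 planned enrolments, which is surplus and not an error.

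**Conclusion.** The point holds as a modest, avoidable weakness. A fixed block size stated in the protocol, one list at one site and masking argued from appearance alone could make some allocations partly predictable to people involved in recruitment or care.

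The size rests on an accuracy of inference that the documents do not give. The 11.7 certain allocations of 70 are a ceiling that requires perfect inference and knowledge of the block size. At 70% to 90% accuracy the gain over chance is about 4 to 9 points, and no allocation is certain. The documents do not support the stronger reading that staff can in fact predict allocations, or that the trial's result is compromised. The sample size is unaffected. This is an optional improvement, justified mainly because it costs so little.

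**What to change.** In Section III.2, replace the fixed scheme with permuted blocks of randomly varying even size and similar length, for example 8, 10 and 12. Have the list generated by someone with no part in recruitment or care. Keep the sizes only in the pharmacy's restricted file, and have the protocol say just that block sizes vary and are withheld. Avoid markedly smaller blocks, for the reason shown in the working.

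The cost is one edited sentence and a regenerated envelope list, before enrolment or for the envelopes that remain. The final arms may not be exactly 35/35. In the simulations with 8/10/12, about 59% of trials ended at 35/35, about 38% at 36/34 and 2% to 3% at 37/33, with anything wider rare. The change does not address unmasking itself. Where staffing allows, separating those who recruit from those who see urine output after dosing would help with that.

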3. Inclusion criteria

Define subject eligibility based on scientific rationale and safety considerations. Include the timeframe of data collection for retrospective studies.

Inclusion Criteria

- Subjects 18 years of age or older
- Subjects with intrauterine pregnancy at or beyond 20 weeks of gestation
- Subjects with a diagnosis of hypertensive disorder in pregnancy
- Subjects with persistent (on repeat BP check 15 min apart) severe range blood pressure recordings (systolic BP≥ 160 or diastolic BP≥ 110) with wide pulse pressure (>60 mmHg)
- Subject able to provide informed consent

4. Exclusion criteria

Define exclusion criteria to limit the study population and prevent subjects from being exposed to excess risk by the study. Exclusion criteria should account for warnings, precautions, and contraindications listed in current product labeling.

Exclusion Criteria

- Subjects less than 18 years of age
- Subjects with intrauterine pregnancy less than 20 weeks of gestation
- Subjects with known fetal anomaly
- Subjects with hypokalemia (K <3.0 mEg/L) on admission

Version 2

Protocol Number I

- Subjects with anuria (<50mL urine in 24 hours) or renal failure
- Subjects previously taking diuretics or potassium supplements for any reason
- Subjects with a known allergy/adverse reaction to furosemide
- Subjects who are unable to understand and/or sign the informed consent
- Active labor (≥ 6cm dilated) or epidural in place

5. Vulnerable subjects

Provide justification for the necessary inclusion of vulnerable populations. Vulnerable subjects often need additional protection and certain restrictions and requirements may apply. Children, pregnant women, and prisoner are examples of vulnerable populations.

Preeclampsia exclusively affects pregnant individuals. As such, pregnant subjects should be studied. To protect these patients, consent forms will be collected and we will reiterate that declining study participation will in no way affect the quality of care they will receive.

Section III: Methods and Procedures

1. Methods and procedures

Summarize the research design (observational, randomized, case-study, etc.) and include a schematic diagram if applicable. Provide a sequential list identifying all the procedures of the study, distinguishing between experimental procedures and procedures resulting from routine care. Explain procedures, situations, or materials that may be hazardous and subsequent precautions to reduce subject risk.

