This will be a prospective double-blinded randomized placebo control trial of women ≥20 weeks of gestation with persistent antepartum hypertension (sustained SBP ≥160 or DBP ≥110 mmHg) and a wide pulse pressure (>60 mmHg) who meet all inclusion criteria and have no exclusion criteria. It is routine that laboratory studies are performed on admission for all women with hypertensive disorders. If electrolyte disturbances exist, therapy will not be initiated unless the electrolyte is normalized or repleted.

After informed consent and upon meeting inclusion criteria with severe range hypertension with wide pulse pressure, the study personnel will inform pharmacy personnel who will then randomly assigned the patient to groups by opening the next previously prepared sequential and numbered opaque study envelope. Participants will be randomized to furosemide plus an antihypertensive versus placebo containing normal saline and an antihypertensive. The pharmacy staff will send the assigned treatment. which will be administered by the bedside nurse. The vials containing the treatment will be indistinguishable as both furosemide and normal saline placebo are clear, colorless solutions. Thus, the provider, nurse, and patient will be blinded to the treatment. The choice of antihypertensive will be determined by the primary OB provider. At our institution, this will be one or more of the recommended medications for urgent blood pressure control as outlined by the American College of Obstetricians and Gynecologists Practice Bulletin on gestational hypertension and preeclampsia. These include IV labetalol, IV hydralazine, or immediate-release oral nifedipine. As meta-analyses have not shown that one of the aforementioned antihypertensives is superior than another, and all are reasonable options, the choice of antihypertensive will be left up to the OB

Version 2

Protocol Number I

provider^{8,9}. This will also improve the generalizability of the study as it does not interfere with what is typically done in clinical practice.

As a procedure of the study, patients will have their blood pressure recorded at least every 15 minutes up to one hour after administration of the study drug. Thereafter, as part of routine care, patients in both groups will receive similar antepartum surveillance, including blood pressure and pulse assessment every four hours or more frequently if vital signs are abnormal, daily weight measurement, and daily urinary output measurements.

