Subjects who terminate participation will resume regular care as determined by her primary treatment team. The investigators will discontinue collecting data on the individual and the choice of medications for acute blood pressure control will no longer be influenced by the investigators or study protocol.

Section IV: Risk/Benefit Assessment

1. Risk category (Contact HPHRI if you need assistance determining risk level)
State the risk of participating in the study as either Minimal or Greater than
Minimal. Risk is defined as the potential harm associated with the research that a

Version 2

Protocol Number I

reasonable person would find injurious. Minimal Risk means that the probability or magnitude of harm or discomfort anticipated in the research are not greater than those ordinarily encountered in daily life or during the performance of routine physical or psychological examinations or tests.

Participation in this study presents greater than minimal risk to subjects but not greater than the risks incurred by their existing disease process. As patients admitted with severe preeclampsia are required to have intravenous access, no additional invasive lines would be placed for the sole purpose of administering the study medications. Additionally, furosemide is already used for the aforementioned indication (severe range blood pressure with wide pulse pressure) in pregnant women. As furosemide is an approved drug being used for its approved indication in this study (ACC/AHA [Whelton 2017], risks incurred to the patient are outweighed by the potential benefit of treating a life-threatening condition (severe range blood pressure).

2. Potential risk(s)

Describe any potential risks associated with the study (physical, psychological, sociological, economic, and/or legal). If possible, estimate the probability of a given risk and potential reversibility.

Potential risks associated with participation in this study include the known pharmacologic effect of furosemide, which include fluid/electrolyte loss as well as rare side effects such as.

Cardiovascular: Necrotizing angiitis, orthostatic hypotension, thrombophlebitis, vasculitis Central nervous system: Dizziness, headache, paresthesia, restlessness, vertigo Dermatologic: Acute generalized exanthematous pustulosis, bullous pemphigoid, erythema multiforme, exfoliative dermatitis, pruritus, skin photosensitivity, skin rash, Stevens-Johnson syndrome, toxic epidermal necrolysis, urticaria

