Endocrine & metabolic: Glycosuria, hyperglycemia, hyperuricemia, increased serum cholesterol, increased serum triglycerides

Gastrointestinal: Abdominal cramps, anorexia, constipation, diarrhea, gastric irritation, mouth irritation, nausea, pancreatitis, vomiting

Genitourinary: Bladder spasm

Hematologic & oncologic: Agranulocytosis, anemia, aplastic anemia, eosinophilia, hemolytic anemia, leukopenia, purpura, thrombocytopenia

Hepatic: Hepatic encephalopathy, intrahepatic cholestatic jaundice, liver enzymes increased

Hypersensitivity: Anaphylaxis, anaphylactoid reaction, anaphylactic shock

Immunologic: DRESS syndrome

Neuromuscular & skeletal: Muscle spasm, weakness

Ophthalmic: Blurred vision, xanthopsia

Otic: Deafness, tinnitus

Renal: Interstitial nephritis (allergic), renal disease

Miscellaneous: Fever

Source: https://www.uptodate.com/contents/furosemide-drug information?search=furosemide&source=panel_search_result&selectedTitle=1~148&usa ge type=panel&kp tab=drug general&display rank=1

Version 2

Protocol Number I

3. Protection against risk(s)

Describe how the study will minimize or prevent any potential risks. Techniques to minimize risk include subject monitoring, withdrawal criteria, and follow-up procedures.

Subjects will be monitored for side effects and dosage levels will be adjusted if the subject experiences side effects from furosemide. Subjects will not receive additional furosemide if side effects are deemed significant. Subjects will be allowed to withdraw from the study at any time without consequence. If new information about the study becomes available, subjects will be informed and re-consented if applicable.

4. Potential benefit(s) to the subject

Describe any potential medical benefit(s) for subject participation. State if participation results in no benefit to the subject.

The direct medical benefits to the subject for participating in the study include acute control of severe hypertension, which reduces the risk of stroke, placental abruption, hypertensive encephalopathy, and myocardial infarction. An additional benefit may include prolongation of pregnancy at critical gestational ages which may reduce the risks of prematurity which includes respiratory distress, intraventricular hemorrhage, necrotizing enterocolitis, and metabolic and thermic dysregulation.

5. Alternative to participation

Describe any alternative therapies or courses of action available to the subject if they decide not to participate in the study.

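### The protocol names electrolyte loss as a known effect of furosemide and screens for it before dosing, but plans no electrolyte measurement afterwards, so planned data cannot compare the arms on it

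*Combined protocol and SAP*

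**What the plan says.** **Named risk.** Section IV.2 (Potential risks) opens with "the known pharmacologic effect of furosemide, which include fluid/electrolyte loss" and then turns to a long list of side effects that it calls rare.

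**Before dosing.** Section II.4 excludes "Subjects with hypokalemia (K <3.0 mEg/L) on admission", as well as anuria or renal failure and previous use of diuretics or potassium supplements. Section III.1 says "It is routine that laboratory studies are performed on admission for all women with hypertensive disorders" and adds "If electrolyte disturbances exist, therapy will not be initiated unless the electrolyte is normalized or repleted".

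**After dosing.** The study procedure in Section III.1 is blood pressure at 15, 30, 45 and 60 minutes. Routine care then provides blood pressure and pulse every four hours, or more often if abnormal, plus "daily weight measurement, and daily urinary output measurements". No laboratory test is listed.

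**Safety follow-up.** The Data monitoring text in Section III has nurses and obstetric providers report adverse events, with the sub-investigator also following participants actively. Section IV.3 (Protection against risks) says "Subjects will be monitored for side effects". Neither mentions a laboratory component.

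**Analysis.** The objectives in Section I.1 are systolic and diastolic blood pressure. Section III.2 names no electrolyte or other safety variable.

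**The concern.** The protocol treats electrolytes as important enough to control entry and the start of therapy, then does not return to them once the drug is given. A fall in potassium without symptoms shows only in a blood test, and none is planned. The protection described in Section IV.3 depends on side effects being noticed, while the procedures in Section III.1 do not collect the information that would show this one.

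What is at stake is what the trial can say at the end. Section I.2 states that the authors know of no earlier randomized study of furosemide for antepartum hypertension. Section III classes the study as above minimal risk, and Section IV.1 judges the risks to be outweighed by benefit. A blinded placebo comparison is a good setting in which to measure the named effect. As planned, a report that no electrolyte events occurred could not be told apart from not having looked.

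**Working it through.** **Step 1: the plan's own numbers, for denominators.** Inputs from Section III.2: difference 15 mmHg, SD 20 mmHg, two-sided 0.05, power 80%.

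n per arm = 2 × (1.96 + 0.84)² × 20² / 15² ≈ 27.9, so 28 per arm and 56 in total. Enrolment at 80% retention (Section II.1) = 56 / 0.80 = 70, or 35 per arm. Both figures reproduce, and nothing below alters them. The 35 per arm is an enrolment figure with an allowance for withdrawal and exclusion after consent, so the number dosed may be smaller. I use 28 and 35 as the range.

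**Step 2: what is planned, before and after dosing.**

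| Item | Before study drug | After study drug |
|---|---|---|
| Electrolytes | Admission laboratory studies; potassium exclusion; correction of any disturbance, which implies a re-check in affected women | None listed |
| Fluid balance | Not specified for the study | Daily weight, daily urine output (routine care) |
| Blood pressure | Baseline severe reading | 15, 30, 45 and 60 minutes, then every four hours |
| Adverse events | – | General reporting and follow-up, no laboratory element |
| Named in the analysis | Baseline blood pressure | Blood pressure only |

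Planned post-dose electrolyte values: 0 in the furosemide arm and 0 in the placebo arm. A between-arm change needs a post-dose value in each arm, so none can be calculated from planned data.

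**Step 3: what one recorded post-dose value would give.** If no woman in an arm fell below the potassium level, the exact one-sided 95% upper bound on the rate is 1 − 0.05^(1/n):

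- n = 28: 1 − 0.05^(1/28) = 10.1%
- n = 35: 1 − 0.05^(1/35) = 8.2%

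Missing draws widen this. If only half of 28 women had a later sample (an assumption), n = 14 and the bound is 1 − 0.05^(1/14) = 19.3%.

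**Step 4: change on the continuous scale (illustration).** With a two-sided 0.05 t-test at 80% power, the detectable difference is 0.76 SD at 28 per arm and 0.68 SD at 35. The documents give no SD for potassium. For an assumed SD of 0.3 to 0.5 mEq/L:

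- 28 per arm: 0.76 × 0.3 = 0.23 to 0.76 × 0.5 = 0.38 mEq/L
- 35 per arm: 0.68 × 0.3 = 0.20 to 0.68 × 0.5 = 0.34 mEq/L

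The mean change is therefore the more informative summary, and the count below the threshold is supporting description.

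**The case against.** The strongest reply has four parts.

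- **The entry rules reduce the risk.** Low potassium, renal failure and prior diuretics are excluded, and a disturbance must be corrected before therapy. This stands, but it lowers the risk without measuring it.
- **Safety is watched.** The sub-investigator follows participants actively, and routine care may include blood tests. This also stands, and it rules out one tempting inference: that electrolyte loss could not be detected at all, or would never reach the study team. A symptomatic case, or one found on a test ordered for other reasons, could be reported. Such tests would be ordered case by case, however, and would not give a systematic comparison of arms.
- **Fluid loss is covered.** Daily weight and urine output bear on it in both arms, although neither is a named outcome. The point is confined to electrolytes.
- **The trial makes no comparative safety claim.** Its stated objectives are blood pressure. This limits the importance of the point but does not remove it, because the protocol itself names the effect and weighs risk against benefit.

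Two other readings go too far. A reader might infer that the admission panel is days old at dosing. The documents give no interval: the study procedures place consent before the severe reading, while Section V.1 places first contact at that reading. A reader might also take electrolyte loss to be the main expected harm. Section IV.2 lists it first, with fluid loss, but does not rank it.

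**Conclusion.** The point holds in a limited form: no electrolyte measurement after dosing is planned, so the trial will have no systematic data in either arm on an effect that its own risk section describes as known. The size is zero planned post-dose values in both arms, whether 28 or 35 per arm are counted.

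This rests on reading the routine-care list in Section III.1 as the full description of what happens after dosing. If the hospital routinely repeats electrolytes, the values may exist in the charts, but the plan neither collects nor analyses them. The documents do not support saying that harm would go undetected, or that Sections IV.2 and IV.3 contradict each other; general side-effect monitoring is compatible with the named risk but does not measure this part of it.

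This is a worthwhile, inexpensive improvement. It does not threaten the primary analysis.

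**What to change.** **Section III.1.** For both arms, record the last electrolyte values before study drug and those from the first routine blood draw after it, within a window the investigators set. If electrolytes were not ordered on that sample, request them as an add-on. Require no new draw; record a woman with no sample in the window as missing. The study procedures list one administration, while Section IV.3 refers to dose adjustment and additional furosemide. Those passages must be reconciled so that the reference dose for the window is clear.

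**Section III.2.** Summarise by arm, descriptively: the number measured, the change from the pre-dose value with a confidence interval, and the number below the protocol's own potassium exclusion level (K <3.0) with a confidence interval. No formal test is needed.

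Clinical response to any value stays with the investigators and the treating team.

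**Cost.** A minor amendment, chart abstraction for each woman and some add-on chemistry tests. Timing will vary between women, some values will be missing, and women who leave the study will contribute none after that point, because Section III.5 ends data collection then. The intervals will be wide, as shown above.
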